6.2.1.4.2 Infusion Interruption

Significant events requiring a change in treatment will be managed by immediate infusion interruption of equal or less than 24 hours. Both, infusion interruptions and treatment interruptions greater than 24 hours, have to be documented in the eCRF:

- The subject experiences a DLT as defined in [Section 6.2.1.3](#)
- The subject meets criteria for temporary or permanent discontinuation of investigational product as described in [Section 8.3](#)
- Technical problem with the infusion pump
- The investigational product is incorrectly prepared or administered (eg, overdose)

6.2.1.4.3 Restarting the Infusion

Treatment may resume if the interruption is \leq 21 days and if:

- The interruption occurred due to other reasons than toxicity (technical or logistic reasons; eg, diagnostic measurements). The infusion can be restarted at the same dose and without additional measures.
- The toxicity has resolved to \leq grade 1. The infusion can be restarted according to guidelines presented in [Table 4](#) or [Table 5](#).
- The toxicity occurred during the DLT period or has resolved to grade 2. The infusion can only be restarted in an individual subject with a clear clinical benefit from treatment after consultation with the sponsor on a case-by-case basis.

Restarting the infusion after a treatment interruption requires care. The start should be performed in the hospital with all infusion day 1 specific measures if the reason for the interruption was other than a technical issue or the interruption was $>$ 24 hours independent of reason. Prophylactic treatment with steroid (eg, dexamethasone) is recommended before restarting of AMG 211 if clinically indicated.

Subjects that have had a treatment interruption during cycle 1 should be given the opportunity to complete a total of 14 or 28 days of infusion even though these may not be DLT evaluable subjects.

Subjects that have had a treatment interruption lasting \geq 48 hours from cycle 2 onwards should re-start treatment as a new cycle.

6.2.1.4.4 Permanent Discontinuation

A subject will permanently discontinue treatment with investigational product in the event of:

- Dose-limiting or other unmanageable toxicity. If a DLT occurs in a subject with a clear clinical benefit from treatment a restart at a lower dose can be considered if the toxicity has resolved and after consultation with the sponsor.

- Disease progression documented on 2 consecutive imaging assessments separated by at least 4 weeks as defined by modified irRC ([Appendix D](#)). Subjects who show disease progression on a single imaging assessment and who show global clinical deterioration suggesting that no further benefit from treatment is likely should be discontinued from study treatment.
- Withdrawal of subject's consent
- Subject or investigator not compliant with the study protocol
- Occurrence or progression of a medical condition which in the opinion of the investigator should preclude further participation of the subject in the study

All reasons for treatment discontinuation should be clearly and concisely documented in the eCRF. If a subject has not continued to present for study visits, the investigator should determine the reason and circumstances as completely and accurately as possible.

In any case of premature treatment discontinuation, the investigator should make every effort to perform all examinations scheduled for the EOIP and EOS visits. These data should be recorded, as they comprise an essential evaluation that should be performed prior to discharging any subject from the study and to allow for the evaluation of the study endpoints.

6.3 Other Protocol-required Therapies

All other protocol required therapies including corticosteroids, that are commercially available are not provided or reimbursed by Amgen (except if required by local regulation). The investigator will be responsible for obtaining supplies of these protocol-required therapies. Please also refer to [Section 6.5: Concomitant therapy](#).

6.4 Hepatotoxicity Stopping and Rechallenge Rules

Subjects with abnormal hepatic laboratory values (ie, ALP, AST, ALT, TBL) and/or INR and/or signs/symptoms of hepatitis (as described below) may meet the criteria for withholding or permanent discontinuation of Amgen investigational product or other protocol-required therapies as specified in the Guidance for Industry Drug-Induced Liver Injury: [Premarketing Clinical Evaluation, July 2009](#).

6.4.1 Criteria for Permanent Withholding of Amgen Investigational Product due to Potential Hepatotoxicity

Investigational product should be discontinued permanently and the subject should be followed according to the recommendations in [Appendix A](#) (Additional Safety Assessment Information) for possible drug-induced liver injury (DILI), if ALL of the criteria below are met:

- TBL > 2 × ULN or INR > 1.5
- AND increased AST or ALT from the relevant baseline value as specified below:
 - Baseline AST or ALT value: < ULN
 - AST or ALT elevation: > 3 × ULN
- AND no other cause for the combination of the above laboratory abnormalities is immediately apparent; important alternative causes for elevated AST/ALT and/or TBL values include, but are not limited to:
 - Hepatobiliary tract disease
 - Viral hepatitis (eg, Hepatitis A/B/C/D/E, Epstein-Barr Virus, cytomegalovirus, Herpes Simplex Virus, Varicella, toxoplasmosis, and Parvovirus)
 - Right sided heart failure, hypotension, or any cause of hypoxia to the liver causing ischemia
 - Exposure to hepatotoxic agents/drugs or hepatotoxins, including herbal and dietary supplements, plants, and mushrooms
 - Heritable disorders causing impaired glucuronidation (eg, Gilbert's Syndrome, Crigler-Najjar syndrome) and drugs that inhibit bilirubin glucuronidation (eg, indinavir, atazanavir)
 - Alpha-one antitrypsin deficiency
 - Alcoholic hepatitis
 - Autoimmune hepatitis
 - Wilson's disease and hemochromatosis
 - Nonalcoholic Fatty Liver Disease including steatohepatitis (NASH)
 - Non-hepatic causes (eg, rhabdomyolysis, hemolysis)

If an alternative cause for hepatotoxicity is identified or less stringent conditions developed than what are noted above, determine (based on patient population and/or severity of the hepatotoxicity or event) if Amgen IP and other protocol-required therapies should be withheld or permanently discontinued, as deemed appropriate for the safety of the subject.

6.4.2 Criteria for Conditional Withholding of Amgen Investigational Product due to Potential Hepatotoxicity

For subjects who do not meet the criteria for permanent discontinuation of Amgen investigational product outlined above and have no underlying liver disease, and

eligibility criteria requiring normal transaminases and TBL at baseline or subjects with underlying liver disease and baseline abnormal transaminases, the following rules are recommended for withholding of Amgen investigational product and other protocol required therapies:

- Elevation of either AST or ALT according to the following schedule:
 - Baseline AST or ALT value: Any AST or ALT elevation: $> 8 \times \text{ULN}$ at any time
 - Baseline AST or ALT value: Any AST or ALT elevation: $> 5 \times \text{ULN}$ but $< 8 \times \text{ULN}$ for ≥ 2 weeks
 - Baseline AST or ALT value: Any AST or ALT elevation: $> 5 \times \text{ULN}$ but $< 8 \times \text{ULN}$ and unable to adhere to enhanced monitoring schedule
 - Baseline AST or ALT value: Any AST or ALT elevation: $> 3 \times \text{ULN}$ with clinical signs or symptoms which are consistent with hepatitis (such as right upper quadrant pain/tenderness, fever, nausea, vomiting, or jaundice).
- OR: TBL $> 3 \times \text{ULN}$ at any time
- OR: ALP $> 8 \times \text{ULN}$ at any time

AMG 211 should be withheld pending investigation into alternative causes of DILI. If the investigational product is withheld, the subject is to be followed according to recommendations in [Appendix A](#) for possible DILI. Rechallenge may be considered if an alternative cause for impaired liver tests (ALT, AST, ALP) and/or elevated TBL is discovered and the laboratory abnormalities resolve to normal or baseline ([Section 6.4.3](#)).

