4.1 Inclusion Criteria

- 4.1.1 Subject has provided informed consent prior to initiation of any study-specific activities/procedures
- 4.1.2 Male or Female ≥ 18 years of age at the time of informed consent
- 4.1.3 Pathologically documented, diagnosed GI adenocarcinoma (including but not limited to esophageal, gastric, small intestine, colorectal, or pancreatic cancers) that has failed standard treatments or for which standard curative or palliative measures do not exist or are no longer effective
- 4.1.4 At least 1 measurable tumor lesion per modified irRC ([Appendix D](#))
- 4.1.5 Archival tumor tissue available or is willing to undergo biopsy of a tumor lesion before the start of treatment

4.1.6 Adequate hematological, renal, and liver function as follows:

- Absolute neutrophil count (ANC) $> 1500/\text{mm}^3 (1.5 \times 10^9/\text{L})$
- Platelet count $> 100,000 \text{ mm}^3 (100 \times 10^9/\text{L})$
- White blood cell (WBC) count $> 3 \times 10^9/\text{L}$
- Hemoglobin $> 9.0 \text{ g/dL}$
- AST and ALT $< 3.0 \times$ the upper limit of normal (ULN)
- Alkaline phosphatase (ALP) $\leq 2.5 \times$ ULN
- Total bilirubin (TBL) $< 1.5 \times$ ULN (unless subject has suspected Gilbert's syndrome or extrahepatic cause by increased indirect bilirubin fraction)
- Creatinine clearance $> 50 \text{ mL/min}$ calculated by Cockcroft-Gault
- Lipase/amylase $< 1.5 \times$ ULN
- Prothrombin time, partial thromboplastin time, and international normalized ratio (INR) $\leq 1.5 \times$ ULN

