6.2.1.3 Dose-cohort Study Escalation and Stopping Rules Dose-limiting Toxicities (DLT)

A DLT will be defined as any of the following occurring in a subject during the first 28 days of treatment and regarded by the investigators and/or sponsor to be related to AMG 211. The Common Terminology Criteria for Adverse Events (**CTCAE** version 4.03) will be used to assess toxicities/adverse events.

Hematological DLTs

- ANC < $0.5 \times 10^9/L$ for ≥ 7 days
- Febrile neutropenia (fever of unknown origin without clinically or microbiologically documented infection) with ANC < $0.5 \times 10^9/L$ and fever $\geq 38.5^{\circ}\text{C}$
- Platelets < $25 \times 10^9/L$ ≥ 7 days

Non-hematological DLTs

Any AMG 211-related \geq grade 3 non-hematological toxicity excluding

- Nausea and vomiting, which is not refractory to anti-emetics
- Flare-up of pain because of potential increase in tumor volume is not regarded as a DLT
- Cytokine release syndrome manageable with symptomatic treatment and/or infusion interruption of up to 2 days

Subjects are evaluable for a DLT when they have received at least 90% of the planned doses of investigational product within the first treatment cycle (first 28 days of a cycle independent of length of the infusion) with or without the occurrence of a DLT in the 28-day safety observation period.

Any adverse event occurring outside the DLT window that is determined by the investigator to be possibly related to the investigational product, which is seen more frequently or more severe than expected or is persistent despite appropriate management, can be determined to be a DLT upon unanimous decision by the DLRT after review of the adverse event and all available safety data.

For certain toxicities such as laboratory abnormalities without a clear clinical correlation (eg, increase in serum lipase level without signs or symptoms of a clinical pancreatitis), a

discussion between the investigator and the sponsor may take place whether that adverse event should be assessed as a DLT.

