14. APPENDICES

Appendix A. Additional Safety Assessment Information

Adverse Event Grading Scale

The Common Terminology Criteria for Adverse Events Version, version 4 (CTCAE V 4) is available at the following link: http://evs.nci.nih.gov/ftp1/CTCAE/CTCAE_4.03_2010-06-14_QuickReference_5x7.pdf.

Drug-induced Liver Injury Reporting & Additional Assessments

Reporting

To facilitate appropriate monitoring for signals of DILI, cases of concurrent AST or ALT and TBL and/or INR elevation according to the criteria specified in [Section 6.4](#) require the following:

- The event is to be reported to Amgen as a serious adverse event within 24 hours of discovery or notification of the event (ie, before additional etiologic investigations have been concluded)
- The appropriate eCRF (eg, Adverse Event eCRF) that captures information necessary to facilitate the evaluation of treatment-emergent liver abnormalities is to be completed and sent to Amgen.

Other events of hepatotoxicity and potential DILI are to be reported as serious adverse events if they meet the criteria for a serious adverse event defined in [Section 9.2.2](#).

Additional Clinical Assessments and Observation

All subjects in whom investigational product(s) or protocol-required therapies is/are withheld (either permanently or conditionally) due to potential DILI as specified in [Sections 6.4.1](#) and [6.4.2](#) or who experience AST or ALT elevations $> 3 \times \text{ULN}$ are to undergo a period of “close observation” until abnormalities return to normal or to the subject’s baseline levels. Assessments that are to be performed during this period include:

- Repeat AST, ALT, ALP, bilirubin (total and direct), and INR within 24 hours
- In cases of TBL $> 2 \times \text{ULN}$ or INR > 1.5 , retesting of liver tests, bilirubin (total and direct), and INR is to be performed every 24 hours until laboratory abnormalities improve
- Testing frequency of the above laboratory tests may decrease if the abnormalities stabilize or the investigational product(s) or protocol-required therapies has/have been discontinued AND the subject is asymptomatic.

- Initiate investigation of alternative causes for elevated AST or ALT and/or elevated TBL:
 - Obtain complete blood count with differential to assess for eosinophilia
 - Obtain serum total immunoglobulin IgG, Anti-nuclear antibody, Anti Smooth Muscle Antibody, and Liver Kidney Microsomal antibody 1 to assess for autoimmune hepatitis

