 - Obtain serum acetaminophen (paracetamol) levels
 - Obtain a more detailed history of:
 - Prior and/or concurrent diseases or illness
 - Exposure to environmental and/or industrial chemical agents
 - Symptoms (if applicable) including right upper quadrant pain, hypersensitivity-type reactions, fatigue, nausea, vomiting and fever
 - Prior and/or concurrent use of alcohol, recreational drugs and special diets
 - Concomitant use of medications (including non-prescription medicines and herbal and dietary supplements), plants, and mushrooms
 - Obtain viral serologies
 - Obtain creatine phosphokinase, haptoglobin, lactate dehydrogenase, and peripheral blood smear
 - Perform appropriate liver imaging if clinically indicated
- Obtain appropriate blood sampling for PK analysis if this has not already been collected
- Obtain hepatology consult (liver biopsy may be considered in consultation with an hepatologist)
- Follow the subject and the laboratory tests (ALT, AST, TBL, INR) until all laboratory abnormalities return to baseline or normal. The “close observation period” is to continue for a minimum of 4 weeks after discontinuation of all investigational product(s) and protocol-required therapies.

The potential DILI event and additional information such as medical history, concomitant medications, and laboratory results must be captured in corresponding eCRFs.

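### The permanent liver stop in Protocol 6.4.1 has no tier for subjects enrolled with both AST and ALT at or above ULN, which leaves a narrow combined rise with no numeric stop or withholding trigger in 6.4

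*Protocol*

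**What the plan says.** **Entry.** Protocol 4.1.6 admits AST and ALT each < 3.0 × ULN, TBL < 1.5 × ULN (with an exception for suspected Gilbert's syndrome or an extrahepatic cause), and INR ≤ 1.5 × ULN.

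**Permanent stop.** Under 6.4.1 treatment should be discontinued permanently when all of its criteria hold: TBL > 2 × ULN or INR > 1.5; AST or ALT > 3 × ULN, judged from the relevant baseline; and no other cause immediately apparent. The only baseline tier printed is "Baseline AST or ALT value: < ULN". A closing clause covers cases where "less stringent conditions developed than what are noted above". It asks for a decision on withholding or stopping and gives no number.

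**Withholding.** The transaminase rows of 6.4.2 apply to any baseline. They are > 8 × ULN at any time; > 5 to < 8 × ULN for at least 2 weeks, or when enhanced monitoring cannot be kept; and > 3 × ULN only "with clinical signs or symptoms which are consistent with hepatitis". Separate triggers are TBL > 3 × ULN and ALP > 8 × ULN. There is no INR trigger and no combined transaminase and bilirubin trigger.

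**Monitoring and reporting.** Appendix A puts any AST or ALT > 3 × ULN under close observation whatever the baseline. Once bilirubin passes twice ULN, or INR passes 1.5, it adds that "retesting of liver tests, bilirubin (total and direct), and INR is to be performed every 24 hours until laboratory abnormalities improve". It also requires a search for causes and a hepatology consult. Its automatic 24-hour SAE reporting is tied to the Section 6.4 criteria.

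**Grade-based rules.** For other non-hematological toxicity, Table 5 continues the infusion at grades 0–2 with optional interruption. At grade 3 it delays, usually with a restart one dose level lower, and at grade 4 it stops permanently. The protocol does not print the CTCAE cut-offs.

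**The concern.** A combined rise in transaminase and bilirubin (or INR) with no other explanation is the pattern for which 6.4.1 directs a permanent stop. The entry criteria knowingly admit subjects whose AST and ALT are both raised, and for them that rule has no tier. The same laboratory pattern is then watched daily, but no number says when the infusion must be interrupted, so sites can differ.

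The liver matters for this drug. Section 2.2.5 treats other BiTE antibodies as supportive experience for AMG 211, and the dose-limiting toxicities of solitomab included AST, ALT and bilirubin elevations. Section 2.2.4 reports one grade 3 treatment-related ALT increase in the first-in-human study. Because automatic SAE reporting follows the 6.4 criteria, reporting of this pattern is also unclear.

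**Working it through.** The plan states no figure to reproduce. The check applies the rules as written, with enzymes, TBL and ALP in multiples of ULN.

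**Rules.**
- 6.4.1 is met if (TBL > 2 or INR > 1.5), and (baseline AST < 1 or baseline ALT < 1), and peak AST/ALT > 3, and no other cause is apparent. This is the generous reading, in which one enzyme below ULN is enough.
- 6.4.2 is met if peak > 8; or 5 < peak < 8 with duration ≥ 2 weeks or monitoring not kept; or peak > 3 with symptoms; or TBL > 3; or ALP > 8.

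**Cases** (no other cause, no symptoms, ALP normal, monitoring kept). Baselines are AST/ALT 0.9/0.9 and 0.9/1.5 (at least one enzyme below ULN) against 1.5/1.5 and 2.9/2.9 (both raised).

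| Peak AST/ALT | TBL | INR | Duration | 6.4.1, at least one < ULN | 6.4.1, both raised | 6.4.2, any baseline |
|---|---|---|---|---|---|---|
| 4.5 | 2.5 | 1.2 | any | met | not met | not met |
| 5.0 | 3.0 | 1.2 | 8 weeks | met | not met | not met |
| 4.5 | 1.0 | 1.8 | any | met | not met | not met |
| 7.9 | 3.0 | any | 1 week | met | not met | not met |
| 7.9 | 3.0 | any | 2 weeks | met | not met | met |
| 4.5 | 3.1 | any | any | met | not met | met |

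With hepatitis-type symptoms, every row meets 6.4.2. Appendix A close observation and 24-hour retesting apply in every row.

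**Grid.** Both enzymes raised, no symptoms, peak > 3 to 5, TBL ≤ 3, ALP ≤ 8, and TBL > 2 or INR > 1.5. There are 4 × 3 baseline pairs, 5 peaks, 24 TBL/INR pairs (6 × 5 less the 3 × 2 with neither raised), 3 ALP values, 3 durations and 2 monitoring states: 12 × 5 × 24 × 3 × 3 × 2 = 25,920 combinations. None meets 6.4.1 or 6.4.2.

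**What a baseline-multiple tier would cover.** Entry point = max(3, k × baseline). Share of the > 3 to ≤ 5 band covered = (5 − entry) / 2, with a floor of zero.

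| Baseline | Fold rise to reach 3 × ULN | Entry, k = 2 | Covered | Entry, k = 1.5 | Covered |
|---|---|---|---|---|---|
| 1.0 | 3.0 | 3.0 | 100% | 3.0 | 100% |
| 1.5 | 2.0 | 3.0 | 100% | 3.0 | 100% |
| 2.0 | 1.5 | 4.0 | 50% | 3.0 | 100% |
| 2.5 | 1.2 | 5.0 | 0% | 3.75 | 62.5% |
| 2.9 | 1.03 | 5.8 | 0% | 4.35 | 32.5% |

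Reusing > 3 × ULN alone as a permanent stop is too sensitive, since from 2.9 × ULN it is a 1.03-fold rise. A tier of 2 × baseline alone leaves the band uncovered from a baseline of 2.5 × ULN. A withholding trigger is therefore needed alongside any permanent-stop tier.

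**The case against.** The best defence is that the protocol treats raised-baseline subjects differently on purpose. The scope sentence of 6.4.2 names subjects with underlying liver disease and abnormal baseline transaminases, and its rows apply to any baseline. The closing clause of 6.4.1 tells the site to decide by population and severity. Section 6.2.1.4.4 allows a stop for unmanageable toxicity or a precluding condition, and Section 8.3.1 allows removal for a safety concern. The automatic DLT rule covers events "occurring in a subject during the first 28 days of treatment", and the DLRT may classify later ones as DLTs.

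Much of this stands, and it rules out several stronger readings that a reader might infer:

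- *That the subject is unwatched or the protocol silent.* Appendix A and the closing clause say otherwise. What is missing is a number.
- *That any raised enzyme removes the stop.* The tier says AST or ALT, so one enzyme below ULN can still qualify the subject.
- *That 6.4.1 is an absolute mandate.* It says treatment should be discontinued. The language of 6.4.2 is weaker still, as recommended withholding.
- *That the INR arm is wholly uncovered.* It has no upper limit, and a high enough INR could reach a grade at which Table 5 delays or stops treatment.
- *That the event would go unreported.* The investigator can call it serious, and Appendix A sends other hepatotoxicity through the ordinary SAE criteria.

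The defence does not supply a threshold. The any-baseline rows of 6.4.2 contain no combined or INR trigger. Its scope sentence also refers to "eligibility criteria requiring normal transaminases and TBL at baseline", which 4.1.6 does not require, so its application to raised-baseline subjects without underlying liver disease is unclear. The other routes are discretionary or depend on grades the protocol does not print. A grade 3 event under Table 5 leads to a delay and usually a restart, not to the permanent stop of 6.4.1.

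**Conclusion.** The concern holds in a limited form: the permanent-stop rule does not fit part of the population the protocol enrols.

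- **Bilirubin arm.** With both enzymes ≥ ULN at baseline, no hepatitis-type symptoms, no other apparent cause and ALP ≤ 8 × ULN, AST/ALT > 3 to ≤ 5 × ULN with TBL > 2 to ≤ 3 × ULN meets nothing in 6.4.1 or 6.4.2, for any duration.
- **INR arm.** The same holds for INR > 1.5 with TBL ≤ 3 × ULN, unless Table 5 applies through the grade of the INR.
- **Next band up.** AST/ALT > 5 to < 8 × ULN for under 2 weeks with monitoring kept is also outside both sections. The DLT rule and Table 5 may cover it, depending on grade.

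The zone is narrow. Nausea, vomiting or fever consistent with hepatitis triggers 6.4.2 at > 3 × ULN, and nausea and vomiting were among the commonest events in the first-in-human study. A raised baseline may also have a known cause, which would take the case out of 6.4.1 in any event. The documents give no count of such subjects, and none is claimed.

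Two assumptions remain. The printed tier is taken to be complete; its lead-in would fit a longer table, but no second row is visible. The external liver-injury guidance cited in 6.4 is not taken to supply the missing threshold. The amendment is worth making on safety grounds.

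**What to change.** 1. **6.4.2, new withholding trigger for baseline ≥ ULN.** AST or ALT > 3 × ULN and above the subject's own baseline, with TBL > 2 × ULN or INR > 1.5 newly arisen on study, and no other cause immediately apparent. Withhold pending the Appendix A work-up, and state that Appendix A 24-hour SAE reporting applies. The newly-arisen condition matters because 4.1.6 allows exceptions for bilirubin and caps INR at 1.5 × ULN, not at 1.5.
2. **6.4.1, new permanent-stop tier for baseline ≥ ULN.** Set it as a multiple of the subject's own baseline. The sponsor chooses the multiple, for which the documents give no source. If it is 2 × baseline, item 1 is essential.
3. **6.4.3.** Cite 6.4.1 in the bar on rechallenge, in addition to 6.2.1.4.4, which does not name 6.4.1 and allows a restart after a DLT. The practical effect is small because 6.4.1 already makes the stop permanent.
4. **6.4.2 scope sentence.** Replace the wording on eligibility requiring normal transaminases and TBL so that the rules apply to all subjects, and keep the abnormal-baseline arm explicit.

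**Cost.** Wording in 6.4.1, 6.4.2, 6.4.3 and Appendix A, with no new tests or visits. A few subjects with raised baseline enzymes will have treatment withheld or stopped who might otherwise have continued at the investigator's discretion.
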